**Statistical Analysis Plan**

**Sponsor:** Island Pharmaceuticals Ltd  
**Protocol Number:** ISLA101-P01-CT001

If the results for a parameter were reported in different units, the results (including the actual measurement and the normal range limits) will be converted to the Système International (S.I.) unit for the specific parameter and the standardized results/units will be reported. The specific conversion rules will be documented in the SDTM specifications.

Quantitative laboratory measurements reported as '< X', i.e., below the lower limit of quantification (BLQ), or '> X', i.e., above the upper limit of quantification (ULQ), will be converted to X for the purpose of quantitative summaries, but will be presented as recorded, i.e., as '<X' or '>X' in the listing. Any conversion rules that are applied will be highlighted in the footnotes of the affected tables and listings.

Where applicable, parameter names in the outputs will be comprised of the test name and the standardized unit of measure (if applicable), for example, 'Albumin (g/L)'. If a specific test is qualitative or unitless, the parameter name will be the test name only.

For all parameters where a normal range limit value was reported, the normal range will be derived based on the available lower and upper limit values and any reported mathematical symbols. If both a lower and upper limit value is available, the normal range will be presented as '(Lower, Upper)'. If the event that only one of the limit values exist, 'N/A' will be used to replace the 'missing' limit value (for example, '(N/A, Upper)'), unless a direction has been specified, in which case the normal range will be displayed as '(< or > Limit)'.

Quantitative parameter results will be classified as being 'Low' or 'High' depending on whether the result is below or above the normal range limits provided by the analyzing laboratory.

Baseline and change from baseline values will be derived for each parameter (as appropriate) in accordance with the methods defined in Section 5.1.2.

**Table 2    Laboratory Assessments**

Hematology:	Clinical Chemistry:	Urinalysis (dipstick)
Platelet count	ALT (Alanine aminotransferase)	Specific gravity
Red blood cell count (RBC)	Albumin	pH
Hemoglobin	ALP (Alkaline phosphatase)	Clarity
Hematocrit	AST (Aspartate aminotransferase)	Color
White Blood Cell (WBC) count	Blood urea nitrogen (BUN)	Glucose
with Differential:	Calcium	Protein
Basophils (% and Absolute)	Carbon dioxide (CO 2 )	Blood
Eosinophils (% and Absolute)	Chloride	Leukocytes Esterase
Lymphocytes (% and Absolute)	Creatinine	Bilirubin
Monocytes (% and Absolute)	Glucose	Ketones
Neutrophils (% and Absolute)	Inorganic phosphorus	Nitrites
	Magnesium	
	Potassium	Microscopy (if applicable)
	Sodium	Urinary sediment
	Total bilirubin	WBC (White blood cells)
	Total Protein	RBC (Red blood cells)
	Uric acid	Casts
Coagulation		Crystals
Prothrombin time (PT)		Epithelial cells
International normalized ratio (INR)		Bacteria

**Statistical Analysis Plan**

**Sponsor:** Island Pharmaceuticals Ltd  
**Protocol Number:** ISLA101-P01-CT001

**4.1.4 Vital Signs Evaluations**

Vital signs will be performed according to the schedule of assessment (Section 2.5).

The following parameters will be assessed, and measurements and findings will be reported on the 'Vital Signs' eCRF:

- Systolic blood pressure (SBP) (mmHg).
- Diastolic blood pressure (DBP) (mmHg).
- Pulse rate (beats/min).
- Respiratory Rate (breaths/min)
- Temperature (°C)
- Height (cm) (Screening only)
- Body Weight (kg) (Screening only)
- Body Mass Index (kg/m^2) (Screening only)
- Body Surface Area (BSA) (m^2)

Baseline and change from baseline values will be derived for each parameter (as appropriate) in accordance with the methods defined in Section 5.1.2

**4.1.5 12-lead ECG Evaluations**

TriPLICATE and single 12-lead ECG recordings will be performed according to the schedule of assessments (Section 2.5).

The following parameters will be assessed, and measurements and findings will be reported on the '12-lead Electrocardiogram' eCRF:

- Heart Rate (beats/min)
- RR Interval (msec)
- QTcF Interval (msec).
- PR Interval (msec).
- QRS Duration (msec).
- Overall Assessment ('Normal', 'Abnormal Not Clinically Significant [NCS]' or 'Abnormal Clinically Significant [CS]').

Baseline and change from baseline values will be derived for each parameter (as appropriate) in accordance with the methods defined in Section 5.1.2.

**4.1.6 Physical Examination**

Complete physical examinations will be performed in accordance with the schedule of assessments (Section 2.5).

The following body systems will be assessed as part of the physical examination findings and clinical significance as assessed by the investigator ('Normal', 'Abnormal NCS', 'Abnormal CS' including specification of any abnormalities observed) will be recorded on the 'Physical Examination' eCRF:

- General appearance
- Head, ears, eyes, nose, and throat

**Statistical Analysis Plan**

**Sponsor:** Island Pharmaceuticals Ltd  
**Protocol Number:** ISLA101-P01-CT001

- Neck and thyroid
- Lymph nodes
- Cardiovascular system
- Respiratory System
- Gastrointestinal system
- Renal system
- Neurological system
- Musculoskeletal system
- Skin
- Other

## 4.2 Pharmacokinetic Concentrations

Plasma PK samples will be collected at the time points specified in the schedule of assessments (Section 2.5) and Table 3. The PK samples from pre-dose to 96 hours post dose will be considered. The actual sample collection dates and times will be reported on the 'PK Blood Sample Collection' eCRF.

**Table 3 Study Schedule and Sampling Time Points for Pharmacokinetic Analysis**

Study Day		Time Relative to Dose (hours) a	-1	0.5	0.75	1	1.5	2	3	4	5	6	8	10	12	24	36	48	72	96
		Assessment Window (minutes) b	+/-2			+/-5			+/-15			+/-30								
Study Day	Cohorts 1-3	1	X	X	X	X	X	X	X	X	X	X	X	X						
		2																X	X	
		3																	X	
		4																	X	
		5																		X
	Cohort 4	10	X	X	X	X	X	X	X	X	X	X	X	X						
		11																X	X	
		12																	X	
		13																	X	
		14																		X

a: Time from dose begins when first capsule is consumed

b: Vital signs should be assessed prior to PK samples taken

The actual elapsed time (hours) from the reference study drug administration will be calculated as the difference between the actual date time of the sample collection at the nominal time point and the date time of the study drug administration for the specific period.

The time deviation at each time point (minutes), defined as the difference between the nominal (planned) and actual collection times will be calculated as the difference between the nominal collection time point value (i.e., 2 hours post-dose will be 2 hours).

For pre-dose visit, the actual elapsed time from the reference study drug administration and the time deviation will be presented as ' - '.

Deviations from the collection time points will be used to identify out of window samples that may be excluded from the PK analysis (and PK parameter derivation) if deemed to have a major impact on the overall analysis.

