# 6 ALLOCATION, DOSING AND STUDY DRUG ADMINISTRATION

#### **6.1** Randomization Procedures

Subjects will be randomly assigned to a cohort per the clinical research unit's standard randomization, participation, and blinding protocol. Within each cohort, 8 subjects will be assigned in a 3:1 ratio to receive ISLA101 (6 subjects) or placebo (2 subjects). Subjects participating in Cohort 4, the food effect cohort, will maintain the same treatment assignment from their fasted cohort.

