**3.2 Pharmacokinetic (PK) Population**

The Pharmacokinetic (PK) Population will consist of all subjects in the safety population who received at least one dose of ISLA101 and have a pre-dose PK sample and at least 1 post-dose analyzable PK sample (quantifiable Plasma concentration).

The following are reasons for exclusion from the PK Population:

- Subjects did not receive at least one dose of the ISLA101.
- Subjects did not have at least one quantifiable plasma fenretinide concentration.

Subjects will be analyzed according to the treatment they actually receive if this differs from that to which the subject was randomized. Adverse events (e.g., vomiting within 2 hours of dose), protocol deviations or dosing or sampling issues which may potentially impact PK will be assessed on a subject-by-subject basis.

Subjects with sufficient PK concentrations of fenretinide to allow determination of at least 1 PK parameter from ( $C_{max}$  or AUC) will be included in the PK parameters evaluations.

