### 4.3 Pharmacokinetic Parameters

The PK parameters described in this section will be derived based on the plasma concentration-time profiles of fenretinide, MPR and oxo-HPR as observed after the study drug administrations on Day 1 for Cohort 1-3 and Day 10 for Cohort 4 if the data permits using actual timepoints for PK samples. The parameters will be calculated separately for each cohort based on concentrations collected during the specific period.

The PK concentrations will be processed using standard noncompartmental analytical procedures to derive the required parameters. The software used for the analysis will be Phoenix™ WinNonlin® v8.4.0 or greater (Certara, Princeton NJ, USA). Extravascular plasma model with linear up log down trapezoidal rule will be utilized.

The PK parameters described in Table 4 will be derived for the analytes (fenretinide, MPR and oxo-HPR) provided that the required concentration data are available. Supporting PK parameters (used to derive or assess the validity of  $\lambda_z$  and associated parameters) which include Adjusted R^2, number of points for estimation of  $\lambda_z$  or Kel, %AUCextrap and span (ratio of time interval to estimate  $\lambda_z$  to t1/2) will only be listed and not included in the summary tables. %AUCextrap < 20% will be used to validate AUCinf and parameters derived from AUCinf.

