## **6.9 Pharmacokinetic Analyses**

### **6.9.1 Plasma Concentrations**

The analysis of the PK concentration data will be based on the PK population. The PK analysis will be conducted separately for fenretinide and its metabolism (MPR and oxo-HPR) based on the available concentrations data (data permitting). Results will be presented by treatment group and study visit/time point.

The plasma concentrations data for Fenretinide, MPR and oxo-HPR will be summarized by treatment group and nominal collection time points using the statistics described in Section 5.1.3. Below the lower limit of quantification (BLQ) concentration that occurred prior to the first quantifiable concentration will be set to 0 and treated as missing otherwise, for the calculation of summary statistics. The number of BLQ concentrations per treatment group per time point will be included in the summary of concentrations. Zero values will be excluded from the calculation of the geometric statistics. Missing values will be omitted from the calculation of descriptive statistics.

For Cohort 1 to 3, figures of the individual plasma concentrations vs. actual time profiles (all subjects within a treatment group on the same plot) will be presented on a linear and a log-linear scale for 3 analytes (Fenretinide, MPR and oxo-HPR). For the food effect cohort (Cohort 4 and one of the Cohort 1 to 3), the individual fasting and fed (fasted and fed results for all subjects in separate plots, and plots showing each subject's fasting and fed results in the same plot) plasma concentrations vs. actual time profiles will be presented on linear and log-linear scales. BLQ concentrations that occurred prior to the first quantifiable concentration will be set to 0 and treated as missing otherwise in the linear plots. BLQ concentrations will be set to missing in the log-linear plots.

Mean concentration with error bars for standard deviations vs. nominal time curves will be presented on a linear and log-linear scale for 3 analytes (Fenretinide, MPR and oxo-HPR). All treatment groups will be presented on the same plot. Standard deviation bars will also be presented.

All plasma concentration data will be listed, and the listing will include the calculated elapsed time since the study drug administration in the specific period and the time deviations between the actual and planned sample collection times.

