The parameters  $AUC_{inf}$ ,  $AUC_{last}$ , and  $C_{max}$  on fenretinide will also be presented graphically by means of box and whisker plots. The results for all treatment groups will be presented on the same plot. The dose-normalized results for each parameter will also be plotted separately.

All parameter results will be listed based on the PK population and any results that may have been excluded from the summary tables will be flagged.

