## Listing 16.2.6.1 Plasma Pharmacokinetic Concentrations (Pharmacokinetic Population)

Analyte (Unit): Fenretinide (ng/ml) [LLOQ = x.xx ng/mL]

Cohort 1: ISLA101 300 mg Fasted

Subject Number	Time Point	Sample Collection Date Time	Elapsed Time Since Study Drug Administration (Hours)	Time Deviation (Minutes)	Concentration (ng/mL)
xxx-xxx	Pre-dose	YYYY-MM-DD HH:MM	-	-	BLQ
	0.5 hours	YYYY-MM-DD HH:MM	xx.xx	xx	xx.xx
	0.75 hour	YYYY-MM-DD HH:MM	xx.xx	xx	xx.xx
	1 hours	YYYY-MM-DD HH:MM	xx.xx	xx	xx.xx
	1.5 hours	YYYY-MM-DD HH:MM	xx.xx	xx	xx.xx
	2 hours	YYYY-MM-DD HH:MM	xx.xx	xx	xx.xx
	3 hours	YYYY-MM-DD HH:MM	xx.xx	xx	xx.xx
	4 hours	YYYY-MM-DD HH:MM	xx.xx	xx	xx.xx
	5 hours	YYYY-MM-DD HH:MM	xx.xx	xx	xx.xx
	6 hours	YYYY-MM-DD HH:MM	xx.xx	xx	xx.xx
	8 hours	YYYY-MM-DD HH:MM	xx.xx	xx	xx.xx
	10 hours	YYYY-MM-DD HH:MM	xx.xx	xx	xx.xx
	12 hours	YYYY-MM-DD HH:MM	xx.xx	xx	xx.xx
	24 hours	YYYY-MM-DD HH:MM	xx.xx	xx	xx.xx
	36 hours	YYYY-MM-DD HH:MM	xx.xx	xx	xx.xx
	48 hours	YYYY-MM-DD HH:MM	xx.xx	xx	xx.xx
	72 hours	YYYY-MM-DD HH:MM	xx.xx	xx	xx.xx
	96 hours	YYYY-MM-DD HH:MM	xx.xx	xx	xx.xx

BLQ: Below the LLOQ; LLOQ: Lower Limit of Quantification;

Elapsed Time Since Study Drug Administration is calculated as the difference between the Date Time of the sample collection and the Date Time of the study drug administration for the specific period.

Time Deviation is calculated as the difference between the Elapsed Time Since Study Drug Administration and the nominal visit or time point in the specific period.

Program Name: xxx.sas, Creation Date Time: YYYY-MM-DD HH:MM

Page 1 of x

Programmer Note:

Repeat for all treatment groups.

Repeat for the analyte = MPR and oxo-HPR

**Tables, Listings and Figures Shells****Sponsor:** Island Pharmaceuticals, Ltd**Protocol Number:** ISLA101-P01-CT001

Sponsor: Island Pharmaceuticals Ltd  
 Protocol: ISLA101-P01-CT001

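### SAP 4.2 lets the influence of an out-of-window PK sample decide whether it is dropped from Cmax and AUC derivation, with no threshold, decision-maker or timing stated

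*SAP*

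**What the plan says.** SAP 4.2, in the text below Table 3, uses collection-time deviations to pick out samples that fall outside their window. Those samples "may be excluded from the PK analysis (and PK parameter derivation) if deemed to have a major impact on the overall analysis". The clause covers both the PK analysis in general and parameter derivation in particular.

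Four other places bear on it:

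- **Parameters use actual times.** SAP 4.3 says they will be derived "if the data permits using actual timepoints for PK samples". SAP 6.9.2 bases the dose-proportionality and food-effect models on those parameters only.
- **Concentration summaries use nominal times.** Under SAP 6.9.1 the concentrations "will be summarized by treatment group and nominal collection time points using the statistics described in Section 5.1.3", and mean curves are also plotted against nominal time.
- **Other PK problems are handled case by case.** SAP 3.2 says that "dosing or sampling issues which may potentially impact PK will be assessed on a subject-by-subject basis".
- **There is some transparency.** SAP 6.9.1 states: "All plasma concentration data will be listed, and the listing will include the calculated elapsed time since the study drug administration". For parameters, SAP 6.9.2 says "any results that may have been excluded from the summary tables will be flagged".

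SAP 5.7, where a windowing rule could sit, is marked not applicable. Neither document defines a major impact, sets a deviation limit for exclusion, says who decides or when, or plans a sensitivity analysis with all samples retained.

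**The concern.** Under the SAP's wording, timing makes a sample a candidate for exclusion, but influence decides its fate. Of two equally late samples, the one that shifts the answer may go and the other stays. That is selection on influence, even though it is confined to out-of-window samples.

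For Cmax and AUC nothing is gained in return. A late sample entered at its actual elapsed time already sits in the right place on the profile.

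At stake are the power-model slope and the fed/fasted ratio. The footnote to the Table 14.2.4 shell concludes a food effect from point estimates outside 80 to 125%, and the Protocol synopsis says the fed data will support a planned Phase 2 study. Each cohort has six active subjects, so each subject carries a weight of one sixth in a cohort's geometric mean.

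**Working it through.** The plan states no figure on this point, so there is none to reproduce. The check has two parts: whether lateness needs repair once actual times are used, and how far one dropped sample could move a group result.

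**Inputs from the documents.** The 18 sampling times from pre-dose to 96 h (SAP Table 3), linear-up/log-down AUC (SAP 4.3), six active subjects per cohort (Protocol 6.1), and the 80 to 125% rule (Table 14.2.4 shell).

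**Assumed inputs.** A one-compartment oral model, with the half-life, absorption rate ka and residual variability stated at each step. The documents give no values for these.

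**1. Does a late sample damage Cmax or AUC at actual times?** Half-life 8, 16 or 24 h; ka 0.3, 0.6 or 1.2 per h; smooth profiles; peak sample drawn 30 min late.

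- Kept at its actual time: AUClast changes by at most 0.05%, Cmax by -1.1% to +0.7%.
- Peak sample dropped: AUClast changes by -0.03% to -0.2%, Cmax by -0.3% to -2.1%.

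Lateness alone therefore gives no reason to drop the sample.

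**2. Does it damage nominal-time summaries?** In the same models, a 1 h sample drawn 15 min late reads about 10% to 20% high against its nominal time. Here a timing rule is justified.

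**3. Effect of a dropped sample on one subject.**

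- 96 h sample dropped, ka 0.5 per h: AUClast falls by 1 - AUC(0-72)/AUC(0-96) = 1.3%, 7.1%, 11.5% and 14.4% at half-lives of 12, 24, 36 and 48 h.
- Highest sample dropped, half-life 12 to 24 h: the mean ratio of second-highest to highest is 0.93 to 0.94 at 10% residual CV and 0.88 to 0.89 at 20%.
- Highest sample dropped, 25% residual noise, half-life 16 h, ka 0.5 per h, 30% between-subject variability: median Cmax ratio 0.89, 5th percentile 0.67.

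**4. Effect on a geometric mean of six.** If one subject's value is multiplied by r, the geometric mean is multiplied by r^(1/6). The same factor applies to the fed/fasted ratio when that subject's fed value changes and all six pairs are complete.

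- AUClast: 0.987^(1/6) = 0.998; 0.929^(1/6) = 0.988; 0.885^(1/6) = 0.980; 0.856^(1/6) = 0.974. These are falls of 0.2%, 1.2%, 2.0% and 2.6%.
- Cmax: 0.94^(1/6) = 0.990; 0.88^(1/6) = 0.979. These are falls of 1.0% and 2.1%.
- Noisy peak: 0.89^(1/6) = 0.981 at the median; 0.67^(1/6) = 0.935 at the 5th percentile.

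**5. Against the 125% limit.** A ratio of 125/r^(1/6) would be pulled down to 125%.

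| Fall in one fed Cmax | Factor on ratio | Ratio pulled to 125% |
|---|---|---|
| 10% | 0.983 | 127.2% |
| 20% | 0.964 | 129.7% |
| 30% | 0.942 | 132.7% |
| 50% | 0.891 | 140.3% |

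**6. Effect on the power-model slope.** The slope shifts by (x - mean x) ln r / Sxx, where x is the log dose. With six subjects at each of 300, 600 and 900 (nominal levels), mean ln dose is 6.301 and Sxx = 6 × (0.597² + 0.096² + 0.501²) = 3.70. For r = 0.88, ln r = -0.128.

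- Subject in the lowest cohort: (-0.597)(-0.128)/3.70 = +0.021.
- Subject in the highest cohort: (0.501)(-0.128)/3.70 = -0.017.

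**The case against.** The case for leaving the clause alone has several parts.

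- **Few samples should qualify.** Sampling to 96 h takes place during confinement, and Protocol 8 gives PK draws timing priority. This limits how often the clause could be used, but not what it permits when it is used. The figures above hold only if the dropped sample was in fact out of window, which cannot be known in advance.
- **Exclusions leave a trail.** All concentrations are listed with elapsed time and time deviation, excluded parameter results are flagged, and out-of-window procedures are a protocol-deviation category. A reader could detect a dropped sample and recompute. That makes selective exclusion visible; it neither prevents it nor corrects the reported estimate.
- **The wording may mean something milder.** It can be read as referring to a timing error so large that the sample is unrepresentative. That reading is possible, but it still lacks a limit, and it gives no ground for exclusion from an analysis run at actual times.
- **The stakes are modest.** Safety is primary, fasted PK secondary and fed PK exploratory. PK does not drive escalation, and SAP 5.2 sets no hypotheses. This bears on priority and stands.

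A reader might infer two stronger things. One is that the decision will be taken after the results are seen. The SAP gives no timing, so this is left open, not planned. The other is that excluding out-of-window samples is unnecessary everywhere. That fails for nominal-time tables and mean curves, where step 2 shows a real distortion.

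**Conclusion.** The point holds in a limited form. SAP 4.2 permits influence-dependent exclusion within the out-of-window subset, without a prespecified criterion, and for Cmax and AUC that exclusion repairs nothing.

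The likely size is small. One affected subject moves a geometric mean of six by roughly 1% to 2.5% in most of the assumed cases, by 0.2% in the mildest, and by about 6.5% if a very noisy peak is dropped. The 0.88 Cmax case moves the dose-proportionality slope by about 0.02. Such shifts matter mainly if a fed/fasted point estimate lies near 80% or 125%.

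All sizes rest on an assumed one-compartment model with assumed half-life, absorption rate and noise. The textual finding does not depend on them. This is worth correcting because the correction is cheap, but it does not threaten the study's primary objective.

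**What to change.** Delete the impact clause from SAP 4.2 and replace it with:

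> Samples with a recorded collection time enter the NCA at their actual elapsed time regardless of window deviation. A concentration is excluded from the NCA only for a documented assay, sample-handling or dosing problem, decided and recorded before concentrations and treatment codes are reviewed. For nominal-time concentration summaries and mean plots only, samples whose deviation exceeds a prespecified numeric limit are excluded and flagged in the listing.

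Three points go with it:

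- Set the numeric limit separately from the collection windows. The tightest window is ±2 minutes, so excluding every out-of-window sample could remove one a few minutes off schedule from a mean of six.
- In SAP 4.3, state the use of actual times without condition; the present wording can be read as making it depend on the data.
- Complete the definition of time deviation in SAP 4.2, which names only one of its two terms, to match the footnote of Listing 16.2.6.1: "Time Deviation is calculated as the difference between the Elapsed Time Since Study Drug Administration and the nominal visit or time point".

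The exception for documented faults keeps the text compatible with the case-by-case assessment in SAP 3.2. The cost is a few sentences in the SAP and a sample-level exclusion flag in the Listing 16.2.6.1 shell, which has none. No new data are needed.
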